Aim 3: Examine the longitudinal effects of partners' psychophysiological regulation on each other's psychophysiological regulation and on IPV. This aim will explore patterns of change in each partner's psychophysiological regulation as a function of their partner's psychophysiological regulation. More specifically, this aim will investigate whether couple therapy facilitates change by restructuring the relationship in such a way that the change in one partner's behavior helps the other partner regulate their emotions in a functional way.

Principal Investigator: [name]

Protocol Summary for IRB: Feasibility Study of Couple Therapy Treatment for Situational Couple Violence (IRB# 09-13-27)

Study Design

This study has a longitudinal design that requires therapy sessions over 8 weeks, with data collected at every visit. Couple therapy will be conducted using an attachment and affect regulation based therapy approach described below under “Couple Therapy”. Data will be collected in the form of self-report and partner-report measures, as well as physiological screening of the neuroendocrine system. These measures are described below under “Data Collection”. The flowchart for the design of the study is shown below.

After careful screening, eight couples will be enrolled in the study. The couples will be divided into two groups, each consisting of four couples. Distribution of participants to the two groups will be randomized. Group 1 will immediately begin 8 weeks of couple therapy and Group 2 will complete 8 weeks of couple therapy after an 8 week (+ or – 10 days) waiting period is completed.

The pre-test, post-test, and follow-up physiological data collection will be completed at the following times for couples beginning the 8 weeks of couple therapy:

- Baseline Pre-test: Before starting the therapy sessions.
- Post-test: One week (+ or – 5 days) after the end of the therapy session.
- Follow-up: Three months (+ or – 10 days) after the post-test.

The participants that are assigned to Group 2 will also complete the physiological data collection before starting the 8 week waiting period. When participating in the 8 week couple therapy Group, participants will complete a small number of assessments at each therapy session.

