The main hypothesis of the proposed study is that conjoint therapy will gradually promote affect regulation of both partners in orchestration; i.e., improvement in one partners' ability to regulate emotions will have a positive effect in the other partner's ability to regulate emotions. If the outcome of this project supports this hypothesis, these results will provide biologically interpretable and quantitative grounds for the effectiveness of conjoint therapy and pave the way for more comprehensive and large scale effectiveness studies, which, in turn, may establish conjoint therapy as a strategy that will complement "parallel track" treatment in preventing and diminishing IPV.

The physiological processes that were found to link attachment and affect regulation include parasympathetic regulation of heart rate and Hypothalamic Pituitary Adrenal (HPA) axis activity (Beauchaine, 2001; Böhnke, Bertsch, Kruk, & Naumann, 2010; Porges, 2001). There is increasing evidence for the role of HPA axis in the development and enhancement of aggressive behavior in youth as well as adults. Furthermore, cardiac vagal tone, a common physiological marker of the regulation of the Parasympathetic Nervous System (PNS), is correlated with both anxious and disruptive behaviors (Böhnke, Bertsch, Kruk, & Naumann, 2010; Porges, 2001). Putting these observations together, the proposed research further hypothesizes that, through promotion of affect regulation, attachment based couple therapy will enhance regulation of PNS and HPA activity in couples, which in turn will have a diminishing effect on IPV.

In summary, the proposed research integrates research findings on the links between couple therapy, affect regulation, physiological markers of emotion regulation, and IPV to hypothesize and test a novel psychophysiological model for the mechanisms of change induced by couple therapy in the context of IPV.

Target Subject Population

Subject population:

Inclusion criteria:

- 1) This study is open to married, dating, and cohabiting couples.
- 2) Couples will have to be involved in an intimate relationship for at least one year with the current partner.
- 3) Both partners have to be older than 18 years of age at the time they signed the consent form.
- 4) Couples must have mild to moderate forms of situational couple violence.

Principal Investigator: [name]

Protocol Summary for IRB: Feasibility Study of Couple Therapy Treatment for Situational Couple Violence (IRB# 09-13-27)

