- 3) Participants will be excluded from the study if they are not stable on psychiatric medication for more than 12 months.
- 4) Couples will be excluded from the study if there is a discrepancy between partners' reports of violence (received or perpetrated) in the CTS, defined as the difference between the partners' reports of the frequency of a particular act by the same partner. If the difference of the average score of the partners, or for any of the acts in the scale in the CTS is greater than 2, the couple will be excluded from the study. For example, if the female partner reports that the male partner pushed her three times but the male partner reports that he never pushed his partner, the couple will be excluded from the study since the couple will receive a difference score of three for the act of pushing.

Principal Investigator: [name]

Protocol Summary for IRB: Feasibility Study of Couple Therapy Treatment for Situational Couple Violence (IRB# 09-13-27)

- 5) Participants will be excluded from the study if undiagnosed, untreated serious mental illness is suspected during pre-screening. In order to screen participants with severe mental health problems, SCL90 will be used. We will use the cut off 0.885 with the area under the ROC curve with lower and upper bounds of the 95% confidence interval.
- 6) Participants will be excluded from the study if there are indicators of substance misuse. We will use the 16 item SSISA to screen participants' substance use. We'll score only 14 items out of the 16 items, which were selected by the TIP 11 consensus panelists from existing alcohol and drug abuse screening tools. A score of 4 or greater has become the established cutoff point.
- 7) Participants will be excluded if they reported any history of violent legal offences in the past 2 years.
- 8) Participants will be excluded if participants are currently suicidal and/or psychotic and/or patients who are moderately ill (e.g. equivalent of CGI score 3 or greater) at the pre-screening.
- 9) Participants who are not literate or cannot speak English will be excluded. The questionnaires require a 6th grade reading level.

Vulnerable populations:

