Table 2. Assessment schedule

Principal Investigator: [name]

Protocol Summary for IRB: Feasibility Study of Couple Therapy Treatment for Situational Couple Violence (IRB# 09-13-27)

Efficacy & Data Analysis

Data analysis plan

This study is designed to be an initial feasibility study to collect pilot data in pursuit of the following aims:

Aim 1: After the first wave of data collection (pretest), the cross sectional relations among the basic constructs of interest will be examined. These basic constructs are psychophysiological markers of emotion regulation and IPV. In order to understand how these markers are related to violence, t-tests will be used to understand this effect. Each partner's HPA and PNS activity is expected to be directly linked to the violence perpetrated by their partner.

Aim 2: The objective of this aim is to understand whether violence decreases over time following therapy and whether this decrease is accompanied by respective change in physiological markers of emotion regulation. For this purpose, series of chi-square-test will be used as well as qualitative analysis.

Aim 3: In order to represent the interaction between the emotion regulation of partners, links from emotion regulation of each partner to the emotion regulation of the other partner at the next time point are included. Qualitative analysis with a grounded theory approach will be used.

The proposed sample size (8 couples) is chosen as a tradeoff between data collection time and statistical power. Since this is a feasibility study, we chose to start with a small sample size. GPower was used to estimate statistical power for the primary hypotheses. Assuming 8 couples (16 participants), with 4 couples in each group and two waves of data each, the statistical significance can be detected. Specifically, with power = .40, this study can detect an effect size of $f = .80$ (Using t-test statistics). Also chi-square test will be used to test the effectiveness of the intervention with power = .40. With this level of power, this study can detect an effect size of $f = .60$ (Using chi-square statistics).

The PI will continually monitor the study design to determine if there is a need to make modifications or discontinue the study due to lack of efficacy from therapeutic intervention.

Safety

Compensation for research related injury

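### Couples are allocated 4 v 4, but the plan never states the unit of analysis or how within-couple correlation is handled; pooling all 16 partners in an ordinary test would inflate the false-positive rate

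*Combined protocol and SAP*

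**What the plan says.** Under Study Design, the unit placed in the two groups is the couple: "The couples will be divided into two groups, each consisting of four couples". The next sentence speaks of participants ("Distribution of participants to the two groups will be randomized"), but the groups are made up of couples and therapy is given to the couple together. Measurement is per person. Both partners give saliva and heart-rate data (Physiological Measures) and complete questionnaires in separate rooms (Behavioral Measures).

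The Data analysis plan gives the power basis as "Assuming 8 couples (16 participants), with 4 couples in each group and two waves of data each, the statistical significance can be detected". For Aim 1 it says "In order to understand how these markers are related to violence, t-tests will be used to understand this effect". Aim 2 is assigned a series of chi-square tests plus qualitative analysis, and the sample-size paragraph adds: "Also chi-square test will be used to test the effectiveness of the intervention with power = .40". Aim 3, the only aim that links one partner to the other, is analysed qualitatively.

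Two other places bear on the unit. The Purpose section says that Aim 2 looks at the effect of therapy on each partner separately. The Hypotheses section states as the main hypothesis that "conjoint therapy will gradually promote affect regulation of both partners in orchestration".

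**The concern.** Ordinary two-sample t-tests and chi-square tests assume independent observations. Two people who share a relationship, a therapist and every therapy session are unlikely to be independent, and the main hypothesis is that they change together. If both partners enter one between-group test as separate observations, the standard error is too small whenever their outcomes are positively correlated. P-values are then too small and confidence intervals too narrow. The study is meant to give quantitative, objective evidence that couple therapy works, so a nominally significant result from 16 people might rest on only 8 independent units.

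The plan does not rule this out. It mentions 16 participants, names no test that handles the pairing, and leaves the unit unstated. The reader therefore cannot tell what the stated power of .40 refers to.

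**Working it through.** **Inputs from the plan.** 8 couples, 16 people, 4 couples per group; power .40; effect size written as f = .80 for the t-test and f = .60 for the chi-square test.

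**Assumptions, because the plan is silent.** Alpha .05, two-sided; chi-square with 1 degree of freedom and .60 read as Cohen's w; normal outcomes for the t-test; partner correlation ρ from .1 to .7.

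**Step 1: the plan's own power.**

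Chi-square, noncentrality λ = N × w²:
- N = 8: λ = 8 × .36 = 2.88, power .396. This reproduces .40.
- N = 16: λ = 16 × .36 = 5.76, power .670. This does not.

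Two-sample t-test with n per group, noncentrality δ = d√(n/2), 2n − 2 degrees of freedom:
- 8 v 8 people, d = .80: δ = .80 × √4 = 1.60, power .32.
- 4 v 4 couples, d = .80: δ = .80 × √2 = 1.13, power .16.
- 4 v 4 couples, if f = .80 means d = 1.60: δ = 2.26, power .48.
- 8 v 8 people, d = 1.60: power .84.

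None of the t-test results is .40. The chi-square figure fits 8 units; the t-test figure fits neither 8 v 8 nor 4 v 4 at this alpha.

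**Step 2: false-positive rate if 16 partners are pooled between groups.** With two partners per couple, the variance of a group mean is multiplied by 1 + ρ. The large-sample rate is 2 × [1 − Φ(1.96/√(1 + ρ))]. At ρ = .5 this is 2 × [1 − Φ(1.60)] = .110. Simulation (200,000 trials) gives the small-sample values:

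| ρ | Large-sample formula | Pooled t-test, 16 people | t-test on couple means, 4 v 4 |
|---|---|---|---|
| .1 | .062 | .062 | .050 |
| .3 | .086 | .089 | .051 |
| .5 | .110 | .120 | .051 |
| .7 | .133 | .152 | .050 |

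**Step 3: Aim 1.** This is a pretest analysis, not a comparison of the allocated groups. The Data analysis plan relates each person's physiology to violence by that person's partner, so exposure can differ within a couple. Simulating a binary exposure with all 16 people in one t-test at ρ = .5 gives a false-positive rate of about 5% if the two partners' exposures are unrelated, 8% if they agree in 75% of couples, and 12% if they always agree.

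**Step 4: power on a valid unit.** A couple mean has variance (1 + ρ)/2, so the standardised effect is d/√((1 + ρ)/2). At ρ = .5 and d = .80 this is .80/√.75 = .92, and the 4 v 4 t-test has power .20. At d = 1.60 the power is .59. An exact permutation test has C(8,4) = 70 allocations, so its smallest two-sided p-value is 2/70 = .029. The next attainable value, 4/70 = .057, exceeds .05, so its true size is .029. Its power at ρ = .5 is about .12 at d = .80 and .42 to .43 at d = 1.60.

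**The case against.** The strongest reply is that pooling is an inference. The power sentence gives 4 couples per group as well as 16 participants, and the second number may only describe the sample. The Purpose section's wording for Aim 2 suggests separate tests for each partner. Only heterosexual couples are eligible, so that would mean one test for women and one for men, each with one person per couple and each at 5%. The chi-square power also reproduces with 8 units, which suggests that this calculation did not use 16 people. All of this stands. A reader might infer that the plan as written more than doubles the false-positive rate; the documents do not support that. The doubling needs pooling, a two-sided test and a correlation of roughly .4 or more. A one-sided pooled t-test at ρ = .5 gives 9.7%, and a Yates-corrected chi-square gives 4.2% to 6.3%, depending on the event rate.

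The direction of error also depends on the contrast. Aim 2 asks whether violence falls over time, and comparing all 16 people before and after as if independent can be conservative (about 3% at ρ = .5 and a within-person correlation of .5).

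Two further readings should be avoided. Exclusion criterion 4 might look like proof of high partner correlation, but it compares two reports of the same partner's acts. It says nothing about correlation between the partners' own violence, cortisol or vagal tone. The mention of two waves might suggest 32 observations pooled as independent; no section says so.

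The reply does not settle the matter. Separate tests give 4 v 4 people each, so 16 is no longer the basis for power. The separate-partner wording covers Aim 2 only. Nothing in the analysis section states a unit, and the t-test power fits neither candidate.

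**Conclusion.** The point holds in conditional form. The couple is the allocated and treated unit, yet the plan states no unit of analysis and no handling of within-couple correlation, and the tests it names are valid only for independent observations. If the 16 partners are pooled in a two-sided between-group t-test, the false-positive rate is about 6% to 15% for correlations of .1 to .7, against 5% on couple means. At low correlation the effect is small. For Aim 1 at a correlation of .5 it is about 5% to 12%, depending on how often partners' exposures agree. These figures rest on an assumed alpha, sidedness and correlation. The inconsistency in the power statement does not depend on the correlation, but it does depend on alpha .05 two-sided and on how f is read. Feasibility status limits how much this matters but does not remove the need to name the unit.

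**What to change.** In the Data analysis plan:

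- State that group comparisons use one value per couple (for example, the mean of the partners' change scores), compared 4 v 4 by a couple-level t-test with confidence interval or by an exact permutation test. Alternatively, state that women and men are tested separately, with 4 v 4 people per test.
- For Aim 1, use a model with a random couple intercept and small-sample degrees of freedom, or analyse women and men separately.
- State that 16 partners will not enter an ordinary t-test or chi-square test together.
- State the contrast for Aim 2, alpha, sidedness and the effect-size metric, and restate power on the chosen unit.

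This needs no new data or couples. The cost is wider intervals and less favourable stated power: about 20% at d = .80 and 59% at d = 1.60 for the couple-mean t-test at a correlation of .5, and less for the permutation test. Separate tests for women and men avoid the clustering but give two tests per outcome, with roughly a 9% chance of at least one false positive at a correlation of .5.

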The therapy that participants are receiving is not experimental, rather the data collection procedures comprise the research. After 8 weeks of sessions, if participants request additional therapy, the PI will continue to be their therapist until their issue is resolved or they secure another therapist. The PI will also provide referral information in case participants would like to continue with another therapist.

Data and Safety Monitoring

Data Monitoring. The proposed research will include data from approximately 8 couples. The final dataset will include self-reported demographic and behavioral data, along with cortisol levels and heart rate information. All identifiers will be removed from the final dataset prior to release for sharing.

Data will be reviewed after every assessment session. The PI will analyze the data from the first cohort before proceeding with the next to determine if the research should proceed as planned, if PI needs to modify the protocol or discontinue the research (e.g., if Group 2 is doing better than Group 1).

Safety Monitoring. The PI will be responsible for monitoring the safety of the participants. In this study, the welfare of the participants will be of primary concern during treatment. There are a number of interventions cited in the literature for clinicians concerned about violence occurring between partners in between therapy sessions. Several prevention strategies and safety interventions from the literature will be used to prevent and deal with situations that may arise. These strategies and interventions are described in the attached Safety Chart.

Careful assessment will be conducted to understand the dynamics of situational couple violence and potential safety issues that couples are experiencing. The PI will ask questions about whether participants feel they are in danger. If participants are afraid that their partner will retaliate after disclosing sensitive information, these couples will be excluded from the study. Withdrawal from the study will be honored without any coercion.

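### The investigator may change or stop this pilot on an undefined efficacy comparison of four couples with four, which chance alone can often satisfy

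*Combined protocol and SAP*

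**What the plan says.** The design is two randomised groups: "The couples will be divided into two groups, each consisting of four couples", and "Distribution of participants to the two groups will be randomized". Under Study Design, "Group 1 will immediately begin 8 weeks of couple therapy and Group 2 will complete 8 weeks of couple therapy", in Group 2's case after a wait of 8 weeks, plus or minus 10 days. The post-test comes one week (plus or minus 5 days) after therapy ends. The Couple Therapy section has the investigator conduct all therapy.

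Two places allow the study to be altered or ended on results:

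- Data and Safety Monitoring, under Data Monitoring: "Data will be reviewed after every assessment session". Then: "The PI will analyze the data from the first cohort before proceeding with the next to determine if the research should proceed as planned", or "if PI needs to modify the protocol or discontinue the research (e.g., if Group 2 is doing better than Group 1".
- Efficacy & Data Analysis, at the end of the Data analysis plan: the investigator watches the design continually for a need to modify it or "discontinue the study due to lack of efficacy from therapeutic intervention".

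Neither place names the outcome, the time point, the size of difference, a test, a limit on the number of looks, or anyone other than the investigator who takes part in the decision.

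**The concern.** The example given for changing or stopping is that waiting couples look better than treated couples. With four couples per group and no margin, that ordering arises easily by chance, even when the therapy works. The same person gives the therapy, knows the groups, analyses the data and decides.

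The example points against therapy, so the main risk is that a useful pilot is changed or ended on noise, more than that a benefit is falsely claimed. The Data analysis plan describes an initial feasibility study meant to collect pilot data. An early end would forfeit some of those data and could withdraw the therapy planned for Group 2.

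There is also a question of order: the analysis must precede the next cohort, yet Group 2's start is tied to the length of its wait.

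**Working it through.** **The plan's own figure.** The plan gives no error rate for this look. Its only related figure is power .40 for the final tests, with no alpha stated.

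- Chi-square, effect .60, 1 df, alpha 0.05 (assumed): power 0.396 with N = 8 couples, which reproduces .40; 0.670 with N = 16 participants.
- t-test, .80 read as d, two-sided 0.05: 0.160 for 4 v 4 and 0.320 for 8 v 8. One-sided 0.05: 0.261 and 0.451. Reading f = .80 as d = 2f = 1.6, 4 v 4, two-sided: 0.476. Of the independent-group settings tried, only d = .80, 4 v 4, one-sided 0.10 comes close (0.410).

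The t-test figure is therefore not reproduced at alpha 0.05. That is a separate matter and does not enter the calculation below.

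**Chance that Group 2 leads, one continuous measure.** Inputs: 4 v 4 couples, randomised (Study Design). Assumption: any numerical lead counts as doing better. Let d be the true benefit of therapy in SDs of couple-level values.

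- SE of the difference = sqrt(1/4 + 1/4) = 0.707 SD
- P(Group 2 leads) = Phi(-d / 0.707)

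| True d | d / 0.707 | P(Group 2 leads) |
|---|---|---|
| 0 | 0 | 0.500 |
| 0.5 | 0.707 | 0.240 |
| 0.8 | 1.131 | 0.129 |
| 1.6 | 2.263 | 0.012 |

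The last two rows are the two readings of the stated f = .80. The 0.500 needs only that the groups are exchangeable under no effect; a simulated lognormal outcome gives the same value. Treating partners as independent (8 v 8) leaves 0.500 unchanged and gives 0.159 at d = 0.5 and 0.055 at d = 0.8.

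**Other outcome types, no effect.**

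- Yes/no per couple: P(strict lead) = (1 - P(tie)) / 2. At a rate of 0.5, P(tie) = 70/256 = 0.273, giving 0.363. At a rate of 0.1, P(tie) = 0.518, giving 0.241. Over rates 0.1 to 0.65 the range is 0.24 to 0.36.
- Poisson counts with mean 1, 2 or 3 per couple (simulated): 0.43, 0.45, 0.46.
- A lead on any one of k measures: if independent, 1 - 0.5^k, which is 0.75 for two and 0.97 for five. At correlation 0.6 (simulated), 0.65 and 0.80. The Behavioral Measures list alone has 13 questionnaires.

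**What a threshold would do.** A one-sided 5% t-test on couple values has 6 df and critical value 1.943. Group 2 would need an observed advantage of 1.943 x 0.707 = 1.37 SD, and the chance rate under no effect would be 5%. At one-sided 10% the advantage needed is 1.02 SD.

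**Schedule.** Assumption: both groups start on day 0.

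- Group 1 post-test, therapy ending on day 56: 56 + 7 = day 63, window 58 to 68.
- Group 1 post-test, eighth weekly session on day 49: 49 + 7 = day 56, window 51 to 61.
- Group 2 start: day 56, window 46 to 66.

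At nominal dates the post-test is 7 days after Group 2's start, or on the same day. The largest gaps available are 66 - 58 = 8 days and 66 - 51 = 15 days, and each needs the earliest post-test together with the latest Group 2 start.

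**The case against.** The strongest reply is that this is a judgement in a small feasibility study, where learning from the first cohort is legitimate, and that the outcome is partner violence. The Conflict Tactics Scale is used throughout the study, and the Risks section names escalation of conflict. Waiting couples doing better than treated couples can therefore be a sign of harm. This stands, and it shapes the fix: a reader might infer that every between-group comparison should be deleted, but that could remove a harm signal.

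Four other stronger readings are tempting and are not supported:

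- **That the plan contains a rule on the sign of the difference that halts the study half the time.** Group 2's lead is given as an example within a judgement, and doing better is not defined. The 50% holds for any lead on one continuous measure without ties. Aim 2 plans chi-square tests, so outcomes with ties are plausible and the figure may be lower.
- **That rates of non-significance measure the problem** (60% at the stated power of .40; 84% for a two-sided 4 v 4 t-test at d = 0.8). Neither monitoring sentence ties action to a significance test.
- **That a change after the look makes the randomised comparison uninterpretable.** The randomised contrast is 8 weeks of therapy against 8 weeks of waiting, and it is largely observed before a between-cohort change could take effect. Such a change falls mainly on Group 2's therapy phase and later follow-up. Only the continual-monitoring sentence could act during the contrast.
- **That the schedule leaves no time for the look.** Favourable window extremes leave 8 to 15 days, and data are also collected at therapy sessions. The flow chart and assessment table are not visible in the text, so the timing rests on the prose alone.

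None of this supplies the missing endpoint, time point or margin.

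**Conclusion.** The concern holds as a defect in the efficacy grounds for changing or stopping the study. As written, the treating investigator may act on an efficacy impression from 4 v 4 couples with nothing fixed in advance. If any numerical lead counts, Group 2 leads under no effect in 50% of studies on one continuous measure, in about 24-46% where ties occur, and in 65-97% if a lead on any of two to five measures counts. With a therapy that works, the chance is 24% at d = 0.5 and 13% at d = 0.8, or 1.2% if the stated f = .80 means d = 1.6. These are chances that the example condition is met; the text then permits action without requiring it.

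The figures assume equal randomised groups, couple-level values and, for d above 0, normality. First cohort is not defined; 4 v 4 is the natural reading because the example compares the two groups. The schedule conflict is real at nominal dates, assuming a common start, and eases only at window extremes. This should be corrected before enrolment.

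**What to change.** - **Data analysis plan, last sentence:** remove lack of efficacy as a ground for modifying or stopping this pilot. State that efficacy is analysed once, after the last planned assessment.
- **Data Monitoring:** remove a mere numerical lead of Group 2 as an efficacy trigger. Limit the between-cohort review to data completeness and safety, including any worsening of violence in treated couples. The safety criterion is for the investigator and IRB to set; none is proposed here.
- **Timing:** define first cohort and reconcile the date of that review with the Group 1 post-test window and the Group 2 start window.
- **If an efficacy comparison is kept:** name its endpoint, time point and threshold in advance, and report its error rates. The one-sided 5% couple-level t-test above is an illustration; the 1.37 SD it requires shows how little such a look can detect at this size.

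The cost is a few sentences of protocol text, and the loss of an early efficacy stop that carries little information with eight couples. Safety oversight is not reduced.
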